## **9.0 ADVERSE EVENT REPORTING**

### **9.1 Potential treatment hazards**

9.1.1 Injury to perioral structures during the surgical procedure. Use of the robot in transoral surgery has been demonstrated to be safe in a limited data set. However, the use of oral instrumentation for access to base of tongue resections can result in injury to teeth, gums and/or the tongue. The standard risks of surgery include post operative pain and discomfort, bleeding, infection, post operative pneumonia, laryngeal and pharyngeal swelling, difficulty in swallowing, injury to nerves and blood vessels failure to perform resection and adverse reactions or complications from anesthesia. Although very rare, with any surgery there is a risk of life threatening events that may result in persistent or significant disability/incapacity or death. In some cases, a feeding tube may be placed to ensure adequate nutrition and fluid intake. On rare occasions, severe throat edema may require prolonged intubation or re-intubation. There is also a rare risk for instrument breakage and power outage resulting in a shutdown of transoral diagnostic and therapeutic surgical equipment. UAB has backup precautions for these types of situations. It is felt that the use of the robotic assisted surgery will not add additional risks to the standard surgical risks.

9.1.2 Need for additional surgery in cases where TORS cannot be adequately performed.

9.1.4 Confidentiality: As a participant in a UAB protocol that collects data on patients including personal information and disease related information, there is a potential for breach of patient confidentiality.

### **9.2 Reporting adverse events**

#### **9.2.1 Expedited reporting methods**

Unexpected or serious adverse events (SAE) are to be reported immediately to [name] [contact]; UAB Paging Operator [contact]. The SAE reporting period begins with signing of the informed consent. Any event that is both serious and unexpected must be reported to UAB's Institutional Review Board for Human Use within 24 hours after the investigator's initial receipt of the information. A written report must follow in 10 working days of the report.

#### **9.2.2 Adverse event reporting definitions**

In the event of an adverse event the first concern will be for the safety of the subject. Serious adverse events to be reported is

defined as any sign, symptom or medical condition that emerges during surgery through a period of 30 days following surgery that (1) was not present prior to surgery and is not a chronic condition that is in the patient's medical history OR (2) was presented prior to surgery but worsened as a result of surgery, AND that meets any of the following regulatory serious criteria:

- Results in death
- Is life-threatening
- Requires or prolongs inpatient hospitalization
- Is disabling
- Is a congenital anomaly/birth defect
- Is medically significant or requires medical or surgical intervention to prevent one of the outcomes listed above.

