#### **9.2.4 Safety Monitoring**

- [name] will be responsible for review of the data. If at any time it is determined that the risks of participation outweigh the benefits, the study will be reviewed by [name] and the research staff.
- Participant information and adverse events will be evaluated as deemed necessary at the meetings of the Office of Clinical Research for the UAB Division of Otolaryngology – Head and Neck Surgery.
- All events determined to be Serious Adverse Events, whether related to the study procedure or not, will be reported to the Institutional Review Board at UAB.

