### **10.0 SUBJECT EVALUATIONS**

#### **10.1 Baseline evaluations:**

1. Routine medical exam prior to surgery.
2. Dysphagia survey prior to surgery.
3. OSAHS evaluation

**10.2** Pain Diary to be completed by participant daily starting with the day of surgery through 2 weeks post op.

**10.3** Routine follow up exams for three months: (post operative exam and three month follow up exam)

1. Routine medical exam.
2. Assessment for adverse events.
3. Dysphagia survey.
4. OSAHS evaluation (including sleep study if allowed by participant's insurance).

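### Section 5.0 reviews the records only of patients who finish the study forms, which can bias the safety description; separately, 9.2.1 and 9.2.2 start SAE reporting at different points

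*Protocol*

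**What the plan says.** **Record review.** Section 5.0 sets out a two-week pain diary starting on the morning of surgery, and the MDADI swallowing questionnaire before surgery, at the post-operative visit and at about three months. It then says that the medical record review covers those participants who complete the diary and the questionnaire. Section 8.0 describes a review of hospital and clinic records from the routine post-operative period, meant to show what the procedure does to the patient for better or worse. It names no population and sets no completion condition. Section 5.0 also makes safety, alongside efficacy, an aim of the trial, which plans 40 patients.

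**SAE timing.** Section 9.2.1 states: "The SAE reporting period begins with signing of the informed consent". It gives no end. Section 9.2.2, the only definition in the protocol, covers "any sign, symptom or medical condition that emerges during surgery through a period of 30 days following surgery". The condition must also be one that "was not present prior to surgery and is not a chronic condition", or one that "was presented prior to surgery but worsened as a result of surgery". Section 9.2.4 adds: "All events determined to be Serious Adverse Events, whether related to the study procedure or not, will be reported to the Institutional Review Board".

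**The concern.** The two forms are filled in by the patient, and whether they are finished is known only after surgery. Making their completion the condition for the record review selects patients on something that the surgical outcome can influence. Section 3.0 says that post-operative dysphagia can lead to aspiration pneumonia, malnutrition and dehydration. Patients with these complications could plausibly stop a daily diary or miss a later questionnaire. They are the patients whose records matter most for safety.

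The SAE sections raise a lesser problem. Staff who have to classify a serious event between consent and surgery find it inside the reporting period but outside the definition, and the text does not settle which governs. Little is at stake before surgery, where the study adds only a survey and routine evaluation, so this is mainly a matter of reporting compliance.

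**Working it through.** The protocol states no figure to reproduce. The check sets the sections side by side, with one piece of arithmetic for scale.

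**A. Record review**

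1. Population: section 5.0 gives those who complete both forms; section 8.0 states no limit. Section 5.0 is the only one that says who is reviewed, so a reader who follows the protocol literally would apply its restriction.
2. Meaning of completion: the protocol does not define it. If it means all time points, a patient who dies or withdraws before about three months is outside the review. If it means less, fewer patients are lost, but some can still be.
3. Scale: let n of the 40 planned patients be reviewed and x of them have a given complication. With nothing known about the other 40 − n, the proportion among all 40 lies between x/40 and (x + 40 − n)/40. The width is (40 − n)/40. For one patient not reviewed, 1/40 = 2.5 percentage points. This assumes that all 40 are enrolled and that the review is the only source, so it is an upper limit.
4. Direction: the reviewed patients give x/n. This is too low whenever the complication is more frequent among unreviewed than among reviewed patients, which is the expected direction if complications cause non-completion.

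The protocol gives no completion rate, so the number of patients affected cannot be estimated.

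**B. SAE window**

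| Onset of a serious condition | 9.2.1 period | 9.2.2 definition |
|---|---|---|
| Consent to surgery | Inside | Outside, unless surgery worsens it |
| Surgery to day 30 | Inside | Inside, if a limb is met |
| After day 30 | No end stated | Outside |

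Only the first row is a conflict. The routes left for an event in that row are these:

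- Unexpected: section 9.2.1 begins "Unexpected or serious adverse events (SAE) are to be reported immediately to" a named contact, so the internal report applies.
- Serious and unexpected: section 9.2.1 continues "Any event that is both serious and unexpected must be reported to" the IRB, within 24 hours. This speaks of any event and repeats no surgical window, so it can be read to cover the interval before surgery. It can also be read to take its meaning of serious from 9.2.2, which would exclude that interval.
- Serious but expected: the 24-hour rule does not apply. Section 9.2.4 covers events determined to be SAEs and so leads back to 9.2.2. Whether the internal report applies depends on the same choice of reading.

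**The case against.** **On the record review.** Section 8.0 names no population, so it can be read as giving the period, sources and purpose of the review while section 5.0 says who is in it. On that reading the two do not contradict each other. This is fair, but it does not remove the difficulty: the restriction in 5.0 then governs, and it selects on completion. It can also be said that the review is not the only safety source. Section 3.0 draws on data from scheduled visits, section 10.3 has adverse events assessed at each exam, and section 9 covers SAE reports, none of which requires both forms to be finished. This stands as a mitigation. It does not replace the review that section 8.0 relies on to find harms, and a patient who stops the forms may also miss visits.

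**On SAE timing.** The hazards listed in section 9.1 are nearly all surgical or anaesthetic, so few serious events before surgery would count as expected, and an unexpected one may already reach the IRB under 9.2.1. That stands, and it keeps this part small.

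**Stronger readings that a reader might infer.** One is that the day-30 end contradicts section 10.3, which provides for "Routine follow up exams for three months: (post operative exam and three month follow up exam") with adverse events assessed at each. The documents do not support this. Section 9.2.1 is silent on the end and 9.2.2 can supply it, and assessing adverse events for longer than the SAE reporting window is not inconsistent. Expressing the days after day 30 as a share of follow-up would measure calendar time, not events or harm. Another is that serious events before surgery go wholly unreported; the 9.2.1 wording on unexpected events tells against that.

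**Conclusion.** Two parts hold, and both are minor.

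The main one is the completer-only record review in section 5.0. Followed as written, it can drop patients with complications from a safety description that the same section makes an aim, and the likely bias is towards understating harm. At most 2.5 percentage points of a complication proportion are at stake per unreviewed patient, on the assumptions of 40 enrolled patients and no other source. The actual effect depends on how many do not complete the forms and why, which the documents do not say. That complications lead to non-completion is plausible but is an assumption.

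The second is a wording conflict over when SAE reporting starts: consent in 9.2.1, surgery in 9.2.2. It leaves serious events before surgery with an unclear status, above all those that are not unexpected. The documents do not show which start was intended.

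**What to change.** 1. Change section 5.0 so that the medical record review covers every enrolled patient, as far as consent allows, whether or not the diary and questionnaire are complete. State the same population in section 8.0.
2. Report how many patients did not complete each form.
3. Reconcile sections 9.2.1 and 9.2.2 to one SAE window with a stated start and a stated end, and align the limbs that refer to the state before surgery with that start. If the 30-day end is intended, say so in 9.2.1 as well.

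The cost is a few sentences and a chart review for those of the 40 patients who do not finish the forms. No visit, procedure or sample-size change is needed.

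### Section 9.2.2 counts a serious worsening of a pre-existing condition as an SAE only if it is attributed to surgery, which does not fit Section 9.2.4's reporting of SAEs regardless of relatedness

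*Protocol*

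**What the plan says.** Section 9.2.2 builds the reportable SAE from three parts.

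- **Time window.** The event "emerges during surgery through a period of 30 days following surgery".
- **One of two limbs.** Under limb (1) the condition "was not present prior to surgery and is not a chronic condition that is in the patient's medical history". Under limb (2) it "was presented prior to surgery but worsened as a result of surgery".
- **Seriousness.** The second part is joined to the list of serious criteria by "AND that meets any of the following regulatory serious criteria". The list includes death, a threat to life and hospitalization.

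Section 9.2.4 then sets the reporting rule: "All events determined to be Serious Adverse Events, whether related to the study procedure or not, will be reported to the Institutional Review Board". Section 5.0 gives safety, alongside efficacy, as something the study evaluates.

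**The concern.** The usual practice is to decide first whether a serious event happened and then, as a separate item, whether it was related. Limb (2) reverses that order for conditions that existed before surgery, because attribution to surgery becomes part of what makes the event an SAE. An event judged unrelated is then not reported as an unrelated SAE. It is not an SAE at all.

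This matters because the study has one arm at one site. With no concurrent control group, nothing in the data would show that worsening was being attributed too rarely. The only check is a full list of serious events with relatedness noted beside each, and for this class of event the definition does not guarantee such a list. The IRB is also the only body outside the Division that Section 9.2.4 names as receiving safety information.

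**Working it through.** No arithmetic applies. The protocol gives no figure for SAEs to reproduce, and the point rests on the logic of the definition.

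**Inputs.** The window, the two limbs and the serious criteria come from Section 9.2.2, and the reporting rule from Section 9.2.4.

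**Rule as written.** SAE = [limb (1) OR limb (2)] AND at least one serious criterion, within the window.

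**Cases.** Take an event inside the 30 days that meets a serious criterion:

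| Event | Limb (1) | Limb (2) | SAE? |
|---|---|---|---|
| New, not a chronic condition in the history, judged due to surgery | met | not needed | yes |
| New, not a chronic condition in the history, judged not due to surgery | met | not needed | yes |
| Present before surgery, worsens, judged due to surgery | fails | met | yes |
| Present before surgery, worsens, judged not due to surgery | fails | fails | **no** |
| Chronic in the history, quiet before surgery, recurs, judged due to surgery | fails (in the history) | depends on whether it counts as present before surgery | **unclear** |
| Chronic in the history, quiet before surgery, recurs, judged not due to surgery | fails (in the history) | fails | **no** |

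The first two rows show that relatedness makes no difference for new conditions. Rows three and four differ only in the causality judgement, and that judgement alone changes the answer. The result in row four stands even if the outcome is death, because the serious criteria are applied in addition to a limb and not in place of one.

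Row five turns on wording. Read literally, a quiet condition was not present before surgery, so it fails limb (2) even when surgery caused the recurrence. Read loosely, a chronic condition is always present, so it enters through limb (2) and again depends on attribution. The text does not settle which reading applies.

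**Against Section 9.2.4.** Its reporting rule disregards relatedness. For rows one and two that wording does real work. For row four it has nothing to act on, because an unrelated worsening can never have been determined to be an SAE.

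**The case against.** The strongest reply is that the two sections can both be obeyed. Section 9.2.4 takes over only after Section 9.2.2 has decided what an SAE is, and its disregard of relatedness keeps full meaning under limb (1). That is correct. A reader might infer a flat contradiction, but the text supports only a mismatch of intent, confined to pre-existing conditions.

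Other stronger inferences also fail:

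- **That every serious airway event depends on the causality clause because every participant has OSAHS.** Limb (1) works on the sign, symptom or condition, not on the organ system. Pneumonia, bleeding and throat swelling, all listed as hazards in Section 9.1, qualify with no causality test if they were absent before surgery and are not chronic in the history. Only worsening of OSAHS itself, or of another existing disease, goes through limb (2). An early worsening of OSAHS after tongue base surgery could readily be attributed to the operation.
- **That flares of conditions in the history are excluded outright.** Limb (2) can readmit a flare attributed to surgery.
- **That each lost event shifts an SAE rate by 2.5 percentage points.** 1/40 = 2.5% is one patient's share of the planned 40. It does not estimate how many events would be lost, and the only objective in Section 4.0 is the reduction in apnea/hypopnea index. No SAE-rate endpoint is stated.
- **That the surgical team makes the attribution.** Section 9.2.2 does not say who judges it.
- **That the events go unrecorded.** Section 10.3 lists "Assessment for adverse events" at follow-up without these limbs, and Section 8.0 provides for review of the records for good and bad effects. Section 9.2.1 requires prompt internal reporting of events that are unexpected or serious. It also sends events that are both to the IRB, so an unexpected worsening might still get there if serious is read in its ordinary sense.

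These routes are partial. None ensures that a serious worsening that is expected and judged unrelated is counted as an SAE or reaches the IRB. Section 5.0 also ties the record review to participants who complete the diary and questionnaire, which a seriously ill patient may not do. What remains of the reply narrows the point but does not remove it.

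**Conclusion.** The point holds in a limited form. Followed as written, Section 9.2.2 drops one class of serious event from SAE reporting: worsening of a pre-existing or chronic condition within 30 days of surgery that is judged not due to surgery. It leaves a second class unclear, namely recurrence of a chronic condition that was quiet before surgery. For these events Section 9.2.2 does not match the intent of Section 9.2.4. New events are not affected.

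The size is unknown. The document gives no expected number of such events and no prevalence of comorbid disease, so neither a count nor a bias can be calculated. The conclusion assumes that staff apply the limbs as printed. If in practice they report every serious event, nothing is lost, but the text does not tell them to. The defect deserves correction because safety is a stated aim and no control group would expose under-attribution.

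**What to change.** Reconcile Section 9.2.2 with Section 9.2.4 by replacing both limbs with one condition: any sign, symptom or medical condition that is new, recurs, or worsens compared with before surgery, regardless of cause. Leave the serious criteria unchanged, and record relatedness to surgery as a separate item once the event has been counted. Section 9.2.4 then means what it says for every kind of event.

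The change is one sentence plus one field on the event form. Its downside is a few more SAE reports judged unrelated.

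One neighbouring matter should be settled in the same edit, although it is separate and the new sentence does not resolve it. Section 9.2.1 says "The SAE reporting period begins with signing of the informed consent", while the window in Section 9.2.2 opens at surgery.

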#### **9.2.3 Adverse event that does not require expedited reporting**

Any hospitalization for needed additional surgery or additional treatment of the disease for OSAHS or supportive care for disease that is unrelated to surgery such a PEG tube placement does not require expedited reporting.

#### **9.2.4 Safety Monitoring**

- [name] will be responsible for review of the data. If at any time it is determined that the risks of participation outweigh the benefits, the study will be reviewed by [name] and the research staff.
- Participant information and adverse events will be evaluated as deemed necessary at the meetings of the Office of Clinical Research for the UAB Division of Otolaryngology – Head and Neck Surgery.
- All events determined to be Serious Adverse Events, whether related to the study procedure or not, will be reported to the Institutional Review Board at UAB.

### **10.0 SUBJECT EVALUATIONS**

#### **10.1 Baseline evaluations:**

1. Routine medical exam prior to surgery.
2. Dysphagia survey prior to surgery.
3. OSAHS evaluation

**10.2** Pain Diary to be completed by participant daily starting with the day of surgery through 2 weeks post op.

**10.3** Routine follow up exams for three months: (post operative exam and three month follow up exam)

1. Routine medical exam.
2. Assessment for adverse events.
3. Dysphagia survey.
4. OSAHS evaluation (including sleep study if allowed by participant's insurance).

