## 3.0 BACKGROUND AND RATIONALE

Obstructive sleep apnea hypopnea syndrome (OSAHS) is a major public health problem, and studies suggest that the incidence of OSAHS may be even higher than estimated.

Transoral base of tongue resections are commonly preformed to improve symptoms in OSAHS, but among surgeons there is not yet consensus as to the best tongue base operation. The difficulty in treating the tongue base is illustrated by the abundance of available procedures – including genioglossus advancement, hyoid advancement, tongue base suspension, radiofrequency treatment, transoral midline glossectomy, submucosal coblation-assisted tongue base resection and recently; transoral robotic-assisted surgery (TORS) for base of tongue (BOT) resection. We will evaluate TORS BOT resection for use in OSAHS by assessing pre- and post-operative OSAHS scores and comparing them to historical data for alternative BOT operations.

Though routine, BOT resection may result in significant post-operative pain leading to dysphagia. In certain patients, major complications such as aspiration pneumonia, malnutrition and dehydration can occur as a result. Thus, reducing post-operative dysphagia is critical to improving patient outcomes and limiting complication-associated hospital admissions. Several studies have addressed the management of post-operative dysphagia, but none have evaluated TORS BOT resections in OSAHS. Additionally, TORS BOT resections for malignant neoplasms have been previously shown by [name] and [name] to be safe and feasible. An outcome analysis of TORS BOT resections for OSAHS may therefore yield recommendations for reducing patient morbidity and mortality.

To evaluate TORS BOT resection as a treatment for OSAHS; patients will serve as their own controls by undergoing assessment for OSAHS pre- and post-operatively. We will characterize patient morbidities associated with surgical correction of OSAHS by reviewing data collected during regularly scheduled follow-up visits (Appendix A), and by patient pain diaries (Appendix B). In addition, we will independently assess dysphagia using the M.D. Anderson Dysphagia Inventory (Appendix C). Our goal is to improve quality of life for future OSAHS patients undergoing BOT resection.

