#### **4.0 OBJECTIVES:**

##### **4.1 Primary Objective:**

The primary objective of this study will be to determine if base of tongue (BOT) resection with transoral robotic-assisted surgery (TORS) yields improvements in OSAHS with reduction in apnea/hypopnea index.

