#### **5.0 TRIAL DESIGN**

This trial is a single institution non-randomized study to evaluate the efficacy and safety of transoral robotic-assisted surgery (TORS). We propose to use the da Vinci ® Robotic Surgical System which is currently in place at UAB to perform surgical resection in 40 patients with OSAHS.

Patients with OSAHS, who present to the Division of Otolaryngology and are scheduled for base of tongue surgery and enrolled to this study, will be given a pain diary to start the morning of surgery to continue for a total of two weeks following surgery. Patients will also be asked to complete the MD Anderson Dysphagia Index (MDADI) swallowing questionnaire to be done prior to surgery, at their post operative clinic visit and at approximately three months following surgery. A sleep study will be done two to three months following surgery if allowed by participant's insurance carrier. A medical record review will be done on all participants who complete the diary and questionnaire.

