## **8.0 STUDY TREATMENT**

Robotic assisted surgery will be performed in standard fashion. If at any point during the procedure the area for resection is not well visualized, or the resection is compromised, or the procedure is felt to be unsafe (for example potential injury to teeth or gums), the procedure will be aborted. Participants will then be presented an alternative treatment plan for this condition.

Post-operative care and discharge will be performed in the routine manner for OSAHS. Medical records will be reviewed from this period of routine care to determine what effects, good and/or bad, this procedure has on the patient. These records will include hospital and clinic records such as clinic and hospital notes, anesthesia notes, radiological imaging and speech pathology information. Patients will be followed post-operatively using standard practice.

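### Protocol 5.0 ties the medical record review to completing post-operative forms while 8.0 does not, so chart-derived outcomes could be selected on behaviour after surgery

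*Protocol*

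**What the plan says.** The primary objective (4.1) is whether the operation "yields improvements in OSAHS with reduction in apnea/hypopnea index". Section 3.0 makes the comparison within patient: "patients will serve as their own controls by undergoing assessment for OSAHS pre- and post-operatively".

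Two sections describe a chart review.

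- **5.0 Trial Design:** "A medical record review will be done on all participants who complete the diary and questionnaire". The same section says patients "will be given a pain diary to start the morning of surgery to continue for a total of two weeks following surgery", and schedules the MDADI questionnaire "prior to surgery, at their post operative clinic visit and at approximately three months following surgery".
- **8.0 Study Treatment:** "Medical records will be reviewed from this period of routine care". The aim given there is to learn the procedure's good and bad effects. No completion condition is attached. The preceding sentence concerns care and discharge after the operation.

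The assessment schedule lists "3. OSAHS evaluation" at baseline (10.1). At follow-up (10.3) it lists "4. OSAHS evaluation (including sleep study if allowed by participant's insurance").

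**The concern.** Whether a patient fills in a two-week diary and the follow-up questionnaires is settled after the operation, and the operation may influence it. If that decides whose chart is opened, the chart-derived outcomes describe a group selected on a post-treatment variable. Section 3.0 expects significant pain and dysphagia, with major complications in some patients. If those patients return fewer forms, which is plausible but not stated, their morbidity is the part most likely to go unread, and their AHI change could be lost with it.

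The conflict with 8.0 adds a practical problem. Two people abstracting charts could follow different sections and arrive at different analysis sets, each in line with the protocol.

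**Working it through.** The document gives no completion rate, no share of patients with an insurer-permitted sleep study and no AHI variance. The check is therefore a comparison of sections.

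**1. Whose records, and from when.**

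| | 5.0 | 8.0 |
|---|---|---|
| Patients | Those who complete the diary and questionnaire | No condition stated |
| Period | Not stated | Post-operative routine care |
| Pre-operative sleep study report named | No | No |

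The sections differ on patients. Neither says that the pre-operative sleep study report is to be extracted.

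**2. Is the condition in 5.0 a post-treatment one?** The diary starts on the day of surgery and lasts two weeks. Of the three MDADI administrations, one precedes surgery and two follow it. If completion means every form, that is 14 or 15 diary days (depending on how the first and last day are counted) plus 3 questionnaires: 14 + 3 = 17 or 15 + 3 = 18 entries, of which only the first questionnaire falls before the day of surgery. Completion is not defined, and a looser meaning is possible. Even so, any meaning that includes the diary depends on what the patient does after surgery.

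**3. Which data depend on the review?**

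- *Morbidity.* Section 3.0 plans to characterise it from data gathered at scheduled follow-up visits and from pain diaries. Section 8.0 uses chart review to find good and bad effects. Adverse events are also assessed at follow-up visits (10.3 item 2), and serious ones are reported under 9.2, so the review is an important route but not the only one.
- *AHI.* A pre-operative value may reach the study through the baseline evaluation (10.1 item 3) or the eligibility information recorded at entry (6.1, 7.3). A post-operative value may come through 10.3 item 4. The 5.0 review matters where these do not record the figure.

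**4. Who could be affected for AHI?** A patient's AHI change is lost because of 5.0 only if all three of these hold:

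- a post-operative sleep study was done, since without one there is no pair under any review rule;
- the forms are incomplete;
- the pre- or post-operative AHI was not captured by another route.

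None of these frequencies is given. Among the 40 planned patients the number affected may be anything from 0 upward.

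**5. Form of the bias.** Among patients for whom both AHI values exist, let *f* be the fraction lost through 5.0, and *d* the mean change in those kept minus the mean change in those lost. Then mean(kept) − mean(all with a pair) = *f* × *d*. It is zero if *f* = 0 or *d* = 0. The document supplies neither quantity and gives no sign for *d*, so no figure is offered.

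**The case against.** The strongest reply is that 5.0 does not contain the word *only*. It says what is done for completers and excludes nobody expressly, while 8.0 supplies a review without a condition. Section 8.0 also lists anaesthesia notes and imaging, so its scope may be wider than care after discharge. Read together, the sections could mean that every chart is reviewed. That reading is possible, but it leaves the completion clause in 5.0 with no function, and a reader applying 5.0 alone would leave non-completers out. The need to reconcile the two sections stands.

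A reader might go further and infer that the protocol fails to provide for a baseline AHI. The document does not support that. Section 3.0 speaks of assessing OSAHS scores before and after surgery, eligibility requires documented OSAHS, and the baseline evaluation in 10.1 carries no insurance or completion condition. The ordinary reading is that the diagnostic AHI already in the chart serves as baseline. The extra words in 10.3 item 4 explain an insurance limit on the repeat study; their absence from 10.1 is not evidence that no AHI is taken. What remains is that 10.1 could be more explicit. The test type and the permitted age of the baseline study may be fixed in a case report form or an analysis plan that is not shown, so their absence is not an error here.

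**Conclusion.** The point holds as a conflict between 5.0 and 8.0 on whose records are read, with a completion condition in 5.0 that should not govern access to outcome data. It is worth correcting because, followed literally, 5.0 permits selection on post-treatment behaviour, and 3.0 gives a reason why such selection might be related to outcome.

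Its size cannot be stated. It may be tempting to take all 40 patients as the reference group, assume a completion rate and a difference between completers and non-completers, and quote a bias in events per hour. That would overstate the case: both inputs would be invented, pairs exist only where a post-operative sleep study was done, and some AHI values may be recorded elsewhere. The direction is equally unknown.

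The conclusion rests on two assumptions: that the clause in 5.0 is meant as a limit, and that chart review is a working source for at least some outcome data. Under-representation of patients with complications is a possibility, not a finding. The wording of 10.1 item 3 is a minor matter.

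**What to change.** - **5.0:** state that the medical record review is done for all enrolled participants, whether or not the diary and questionnaire are complete, and that it covers the existing pre-operative sleep study report and any post-operative one.
- **8.0:** use the same population and the same list of records.
- **10.1 item 3 (minor):** name the AHI from the existing pre-operative sleep study, with its date and test type. Record the same items under 10.3 item 4 when a post-operative study is done.
- **Consent:** the consent form is not shown. Check that its wording on record review covers all enrolled participants and the pre-operative report.

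The cost is wording in four sections and some chart abstraction. Three fields (AHI, date, test type) at two time points for 40 patients is at most 3 × 2 × 40 = 240 entries, plus review of the charts of participants with incomplete forms. No new test or visit is needed.
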